Constructs	
 Sex, Sexuality Hispanic Origin, Race Address Education Age Health Household Size Income (above or below FPL) Trust in FDA and CDC Nicotine Dependence (FTND) Previous Quit Attempts Smoking Status Quit Intentions Littering Intention Self Efficacy Response Efficacy Positive and Negative Thoughts (Freq, Degree) Current OTP Use Knowledge of HE and Constituents Tripartite Risk Mental Health (K6) Study Information All Previous Day Behavior Qs 	
Previous day behaviors:
 
 Littering on the ground Littering from Car Forgoing Butting out Number of Cigarettes 
Cognitive Questions:
 
 Thinking about chemicals Thinking about risks Thinking about littering Thinking about quitting Message Negative Affect Message Credibility Perceived Effectiveness 	
 Nicotine Dependence (FTND) Quit Attempts Smoking Status Quitline Awareness Quitline Use Quit Intentions Quitline Intention Littering Intention Self Efficacy Response Efficacy Positive and Negative Thoughts (Freq, Degree) Current OTP Use Knowledge of HE and Constituents Tripartite Risk Credibility of FDA Mental Health (K6) Action Expectancies Reactance Talking about messages All Previous Day Behavior Qs Quality Assurance Questions 	
 Nicotine Dependence (FTND) Quit Attempts Smoking Status Quitline Use Quit Intentions Quitline Intention Littering Intention Self Efficacy Response Efficacy Positive and Negative Thoughts (Freq, Degree) Current OTP Use Knowledge of HE and Constituents Tripartite Risk Mental Health (K6) Action Expectancies All Previous Day Behavior Qs

Statistical Principles

Confidence Intervals and P Values

Level of statistical significance

$\alpha=0.05$

Description and rationale for any adjustment for multiplicity and, if so detailing how the type 1 error is to be controlled

NA

Confidence Intervals to be reported

95% CI

Adherence and Protocol Deviations

Definition of adherence to the intervention and how this is assessed including extent of exposure

Compliance with the protocol is assessed as follows:

- Completion of daily surveys, during which participants view intervention stimuli. % Compliance = number of daily surveys completed / 15 (number of surveys supposed to be completed)*100%
- Completion of post test surveys at post 1 and post 2

Description of how adherence to the intervention will be presented

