Gay, lesbian, or bisexual								
Current Cigarette Smoking								
Current smoker								
Nonsmoker								
Fagerstrom Nicotine Dependence Score (FTND)								
Trust in FDA								
Number of Times Participants Viewed a Message During Follow Up								

To update Table 1 see 'Table 1 V1.xlsx' in Analysis Plan folder

Analysis

Outcome definitions

- Quit intentions [Time Frame: day 16] PRIMARY OUTCOME
 - 3 item measure with high reliability, average of the 3 items to create a score range 1-4 (Brewer et al., 2016, 2018; Klein, Zajac, & Monin, 2009)
 - We will compare the differences between pre and post
- Number of cigarettes smoked each day [Time Frame: Measured daily on days 1-15]
 - Continuous, Modified from FTND (Heatherton, Kozlowski, Frecker, & Fagerström, 1991; Storr, Reboussin, & Anthony, 2005)
- Number of cigarettes forgone each day [Time Frame: Measured daily on days 1-15]
 - Continuous, adapted from Brewer 2016 (Brewer et al., 2016)
 - May be zero inflated, if yes, may choose to dichotomize to 0/1
- Number of cigarettes butted out each day [Time Frame: Measured daily on days 1-15]
 - Continuous, adapted from Brewer 2016 (Brewer et al., 2016)
 - May be zero inflated, if yes, may choose to dichotomize to 0/1
- Quit attempts during the study [Time Frame: Measured on days 16 and 32]
 - Adaptation from Fagan (Fagan et al., 2007)
 - May be zero inflated, if yes, may choose to dichotomize to 0/1
- Awareness of quitline [Time Frame: Measured on day 16]
- Recall of quitline phone number [Time Frame: Measured on day 16]
- Use of the quitline during the study [Time Frame: Measured on days 16 and 32]
- Intention to use the quitline [Time Frame: Measured on days 16 and 32]
- Quit intentions [Time Frame: Measured on day 32]
 - 3 item measure with high reliability, average of the 3 items to create a score range 1-4 (Brewer et al., 2016, 2018; Klein et al., 2009)
 - We will compare the differences between pre and post
- Self Efficacy [Time Frame: Measured on days 16 and 32]

- 1 item (“IARC HANDBOOKS OF CANCER PREVENTION,” n.d.; Thrasher, Swayampakala, Borland, et al., 2016; Thrasher, Swayampakala, Cummings, et al., 2016)
- Response Efficacy [Time Frame: Measured on days 16 and 32]
 - 1 item (Thrasher, Swayampakala, Cummings, et al., 2016)

Analysis Methods

Analysis methods will depend on the time point that the outcome was measured. Post test measures will be analyzed differently than measures from the daily surveys, as outlined below.

Post test measures

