Daily Questionnaire Measures

What analysis method will be used and how treatment effects will be presented

Mixed models to account for repeated measures of the same participant.

Any adjustment for covariates

Covariates included in the analysis model (in addition to treatment group):

- Dose of ads (# of times participants viewed a message)

Methods used for assumptions to be checked for statistical methods

Linear mixed model is an extremely flexible for modeling continuous outcomes. It turns out that linear mixed models are robust to violations of some of their assumptions. The followings are the assumptions for linear mixed model: 1) Independent (The outcomes of different people are assumed to be statistically independent of each other.) Note: the outcomes within a person are correlated. 2) Normality (random effects are assumed to be normally distributed with mean zero and the residuals are normally distributed.)

Details of alternative methods to be used if distributional assumptions do not hold (eg normality, proportional hazards, etc)

Because mixed models are robust to violations of some of their assumptions, we do not anticipate needing to use an alternative method.

Any planned sensitivity analyses for each outcome where applicable

None a priori

Any planned subgroup analyses for each outcome including how subgroups are defined

None a priori

Missing Data

Mixed models are appropriate to use and robust to missing data, so we will be able to include everyone who completed at least 1 daily questionnaire.

Additional Analyses

None a priori

Harms

Adverse events were not expected in this trial due to the minimal risks to participants, and no threat to participant health, so this section is not applicable.

Statistical Software

Statistical analyses will be conducted in SAS 9.4 (Cary, NC)

References

Final Dataset: rct_combined_07232018 [location removed]

Data Cleaning Syntax: 01_Create_Analytic_Files.sas [location removed]

Study Protocol: RCT_Protocol_V5 [location removed]

[figure not shown]
Analysis plan compiled according to “Guidelines for the Content of Statistical Analysis Plans in Clinical Trials” (Gamble et al., 2017)

- Brewer, N. T., Hall, M. G., Noar, S. M., Parada, H., Stein-Seroussi, A., Bach, L. E., ... Ribisl, K. M. (2016). Effect of Pictorial Cigarette Pack Warnings on Changes in Smoking Behavior: A Randomized Clinical Trial. *JAMA Internal Medicine*, *176*(7), 905–912. <https://doi.org/10.1001/jamainternmed.2016.2621>

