Behavior Instructions	Please think about yesterday		Behav_Inst	Behav_Inst	Behav_Inst
	What time did you wake up yesterday?	Time	Time#1_Wake_Hour Time#1_Sleep_Hour Time#2_Wake_Min Time#2_Sleep_Min Time#3_Wake_AMPM Time#3_Sleep_AMPM		
	What time did you go to sleep last night?	Time			
Behavior ⁴	How many times yesterday did you dispose of your cigarette butts by dropping them on the ground?	Dropdown list 0-100, 101=refused	Lit1	Lit1	Lit1
	How many times yesterday did you dispose of your cigarette butts by throwing them or dropping them out of the car window?		Lit2	Lit2	Lit2
	How many times yesterday did you stop yourself from having a cigarette because you wanted to smoke less?		Forgo	Forgo	Forgo
	How many times yesterday did you butt out a cigarette before you finished because you wanted to smoke less?		Butt	Butt	Butt
PAGE BREAK					
Cigarettes Smoked ⁷	Yesterday, from the time you woke up until noon, how many cigarettes did you smoke?	Dropdown list 0-100, 101=refused	Cigs_Morn	Cigs_Morn	Cigs_Morn

Construct (Source)	Question Text	Response Option	Pretest Var Name	Post 1 Var Name	Post 2 Var Name
	Yesterday, from noon until you went to sleep, how many cigarettes did you smoke?		Cigs_Afternoon	Cigs_Afternoon	Cigs_Afternoon
PAGE BREAK					
Thinking Instructions ⁴	Overall yesterday, how much did you...		Think	Think	Think
Thinking About Chemicals ⁴	Think about the chemicals in the smoke from your cigarettes?	5=All of the time 4=Often 3=Sometimes 2=Rarely 1=Never	Think_Chem	Think_Chem	Think_Chem
Thinking About Risks	Think about the harm your smoking might be doing to you?		Think_Risk	Think_Risk	Think_Risk
Thinking About Littering	Think about discarding cigarette butts properly?		Think_Lit	Think_Lit	Think_Lit
Thinking about quitting	Think about quitting smoking?		Think_Quit	Think_Quit	Think_Quit
PAGE BREAK					
StudyInfo1	The next few pages give you some more information for what to expect during the study.		StudyInfo1		
PAGE BREAK			PAGE BREAK		
StudyInfo2	Starting tomorrow, you will receive an email at 7am every morning for 15 days from [contact]', with a link to a short survey. You have until 11am to open the link and answer the survey, or you will have to wait until the next one is sent. 		StudyInfo2		
PAGE BREAK			PAGE BREAK		

Construct (Source)	Question Text	Response Option	Pretest Var Name	Post 1 Var Name	Post 2 Var Name

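### The daily-behaviour mixed models leave out the matching pre-test value; adding it would sharpen the overall arm effect at no cost, by an amount that depends on an unstated within-person correlation.

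*Combined protocol and SAP*

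**What the plan says.** The SAP's Outcome definitions list three daily behavioural outcomes: "Number of cigarettes smoked each day [Time Frame: Measured daily on days 1-15", "Number of cigarettes forgone each day [Time Frame: Measured daily on days 1-15" and "Number of cigarettes butted out each day [Time Frame: Measured daily on days 1-15". None is the primary outcome, which is quit intentions at day 16. For the second and third, the same section allows dichotomising to 0/1 if the counts are zero inflated.

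Under Daily Questionnaire Measures the method is "Mixed models to account for repeated measures of the same participant". The one covariate listed besides treatment group is "Dose of ads (# of times participants viewed a message". That section states no random-effects structure, time term or arm-by-time term. It acknowledges that reports within a person are correlated but gives no value.

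The Pre-Test column under Timing of Outcome Assessments includes "All Previous Day Behavior Qs". In Appendix A, the table for pre-test, post-test 1 and post-test 2 gives pre-test variable names to the items behind all three outcomes: Cigs_Morn ("Yesterday, from the time you woke up until noon, how many cigarettes did you smoke") and Cigs_Afternoon, Forgo ("How many times yesterday did you stop yourself from having a cigarette because you wanted to smoke less"), and Butt. The Morning Questionnaire uses the same wording. The Randomization section places allocation at the end of the baseline survey, so these answers precede randomisation.

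**The concern.** Arm varies only between people. A random intercept gives a valid standard error when one person's days are correlated, but it does not remove stable differences between heavy and light smokers from an arm comparison. More daily reports average out day-to-day noise and nothing else. A pre-randomisation measure of the same behaviour can explain part of the stable difference, and the plan collects one for each outcome without using it.

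Nothing else in the daily model does this job. Message viewings are counted after randomisation. The nicotine dependence score appears only in the imputation model for the post-test outcomes. At stake is the width of the confidence intervals for the trial's daily behavioural comparisons.

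**Working it through.** **Inputs from the documents.** 15 daily reports; alpha 0.05; d = 0.25, 80% power and 253 per group (Sample Size section, for quit intentions). The documents give no ICC, no baseline correlation, and no effect size or power target for the daily outcomes.

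**The plan's own figure.** A two-sample t-test with d = 0.25, two-sided alpha 0.05 and 80% power solves to 252.13, so 253 per group; power at 253 is 80.1%. A one-sided test would need 199, so the plan's figure is two-sided.

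**Assumptions.** Linear random-intercept model; daily SD set to 1; ICC between 0.1 and 0.7; the pre-test day correlates with each daily report as strongly as the daily reports do with each other. Message viewings are left out of the calculation.

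**Formulas.** With n per arm and m reports per person:

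- Person-mean variance: v = ICC + (1 - ICC)/m.
- Variance of the arm difference without baseline: (2/n) × v.
- The covariance of the pre-test value with the person mean is ICC, so the share of v that it explains is R² = ICC²/v.
- Ratio of the arm standard error with baseline to without: √(1 - R²). This does not depend on n.
- Illustrative power: noncentral t with noncentrality 0.25 × √(253/2) / √(1 - R²) = 2.81/√(1 - R²), where 0.25 is in SDs of the person mean.

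Example at ICC 0.5, m = 15: v = 0.5 + 0.5/15 = 0.533; R² = 0.25/0.533 = 0.469; SE ratio = √0.531 = 0.729; noncentrality = 2.81/0.729 = 3.86; power 97.1%.

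| ICC | v | Between-person share, ICC/v | R² | SE ratio | Fall in SE | Illustrative power (80.1% without baseline) |
|---|---|---|---|---|---|---|
| 0.1 | 0.160 | 63% | 0.063 | 0.968 | 3% | 82.6% |
| 0.2 | 0.253 | 79% | 0.158 | 0.918 | 8% | 86.4% |
| 0.3 | 0.347 | 87% | 0.260 | 0.860 | 14% | 90.3% |
| 0.5 | 0.533 | 94% | 0.469 | 0.729 | 27% | 97.1% |
| 0.7 | 0.720 | 97% | 0.681 | 0.565 | 43% | 99.9% |

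**Missed surveys.** With 9 reports instead of 15, the SE ratios at ICC 0.2, 0.3, 0.5 and 0.7 are 0.928, 0.873, 0.742 and 0.576, so they change little.

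**Weaker baseline.** If the pre-test day correlates with the daily reports at only 0.7 of the ICC, illustrative power is 83.2% at ICC 0.2 and 85.2% at ICC 0.3.

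**Check by fitting the models.** Simulated random-intercept fits (266 per arm, 15 reports, 15 replicates per ICC) gave mean arm standard errors without and with the pre-test value of 0.050 and 0.043 at ICC 0.3, 0.063 and 0.046 at 0.5, and 0.074 and 0.042 at 0.7. The ratios (0.87, 0.73, 0.57) agree with the formula. The standard error of an arm-by-day slope was unchanged by the covariate.

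**The case against.** The strongest reply is that nothing here is wrong: the outcomes are secondary, and leaving out a baseline value makes the randomised comparison neither biased nor its interval invalid. That stands, and it makes this an efficiency improvement rather than the correction of an error.

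Four further limits also stand.

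- The gain is conditional on figures the plan does not give. At ICC 0.1, or with a weakly correlated pre-test day, it is small.
- The power illustration borrows d = 0.25 and 253 per arm from the quit-intention calculation. Only the standard-error ratios are free of that choice.
- The linear figures do not carry over directly to forgone or butted-out counts analysed as 0/1.
- The point covers the overall arm effect and not an arm-by-day slope. No slope is listed, but the model is not fully specified.

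A reader might also infer that a chance imbalance in baseline smoking, with no stratification factor named, adds a separate harm. It does not. That imbalance is part of the sampling variation that the unadjusted standard error already covers, so counting it again would double the same loss of precision.

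What the objection does not remove is the benefit itself: the items are already collected before randomisation, and using them costs almost nothing.

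**Conclusion.** The point holds as a free improvement to secondary analyses. The daily models adjust for treatment group and message viewings only, so the overall arm effect keeps stable between-person variance that the matching pre-test value could partly remove. Under a linear model, 15 reports and an exchangeable pre-test day, the standard error falls by about 3% at ICC 0.1 and 43% at ICC 0.7. As an illustration only, 80% power becomes about 83% at ICC 0.1, 90% at 0.3 and over 99% at 0.7. These sizes apply to cigarettes smoked.

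Two stronger readings are not supported. The documents do not show that the intervals will be much wider than they need be, because they give no ICC. Nor do they show that the daily arm effects will be biased, because arms are randomised.

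**What to change.** In the SAP, Daily Questionnaire Measures, covariate adjustment, add the matching pre-test value as a fixed covariate in each daily model: Cigs_Morn + Cigs_Afternoon for cigarettes smoked, Forgo for forgone, Butt for butted out. Keep it in any dichotomised version of the last two.

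Before fitting, set code 101 (refused) to missing; if either cigarette item is refused, the sum is missing. Fill any missing baselines by a single imputation that ignores arm, so that no participant with at least one daily survey is dropped.

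The cost is one line of SAP text and one degree of freedom per model, with no new data. Because the SAP already cites a final dataset, record the change as a dated amendment before arm comparisons are examined.

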Appendix A: Study Measures

Constructs by Timeframe

Time	Pre-Test	Morning	Post-Test 1	Post-Test 2
Constructs	
 • Sex, Sexuality • Hispanic Origin, Race • Address • Education • Age • Health • Household Size • Income (above or below FPL) • Trust in FDA and CDC • Nicotine Dependence (FTND) • Previous Quit Attempts • Smoking Status • Quit Intentions • Littering Intention • Self Efficacy • Response Efficacy • Positive and Negative Thoughts (Freq, Degree) • Current OTP Use • Knowledge of HE and Constituents • Tripartite RiskMental Health (K6) • Study Information • All Previous Day Behavior Qs 	
Previous day behaviors:
 
 • Littering on the ground • Littering from Car • Forgoing • Butting out • Number of Cigarettes 
Cognitive Questions:
 
 • Thinking about chemicals • Thinking about risks • Thinking about littering • Thinking about quitting • Message • Negative Affect • Message Credibility • Perceived Effectiveness 	
 • Nicotine Dependence (FTND) • Quit Attempts • Smoking Status • Quitline Awareness • Quitline Use • Quit Intentions • Quitline Intention • Littering Intention • Self Efficacy • Response Efficacy • Positive and Negative Thoughts (Freq, Degree) • Current OTP Use • Knowledge of HE and Constituents • Tripartite Risk • Credibility of FDA • Mental Health (K6) • Action Expectancies • Reactance • Talking about messages • All Previous Day Behavior Qs • Quality Assurance Questions 	
 • Nicotine Dependence (FTND) • Quit Attempts • Smoking Status • Quitline Use • Quit Intentions • Quitline Intention • Littering Intention • Self Efficacy • Response Efficacy • Positive and Negative Thoughts (Freq, Degree) • Current OTP Use • Knowledge of HE and Constituents • Tripartite Risk • Mental Health (K6) • Action Expectancies • All Previous Day Behavior Qs

Pre, Post 1, Post 2

Construct (Source)	Question Text	Response Option	Pretest Var Name	Post 1 Var Name	Post 2 Var Name
Instruction	Please read the consent form on the next page to learn more about our research study and what we are asking participants to do.		Instruction		
Post 1 Instruction	You have now finished the part of the study with daily surveys. This slightly longer survey should take you less than 20 minutes to complete. If you complete the survey, you will be paid an additional \$20 in your incentive check.			Post1_Inst	
Post 2 Instruction	This will be the last survey for this study. Thank you for your participation! This survey should take you less than 20 minutes to complete. If you complete the survey, you will be paid an additional \$20 in your incentive check.				Post2_Inst
PAGE BREAK					

Construct (Source)	Question Text	Response Option	Pretest Var Name	Post 1 Var Name	Post 2 Var Name
Consent Form	[Include current consent form with agreement to participate]		ConsentForm1, ConsentForm_GraphicConsentForm2, ConsentForm3		
PAGE BREAK					
Sex1 ¹	What sex were you assigned at birth, on your original birth certificate? Was it...	1 = Male 2 = Female	Sex1		
Sex2 ¹	Do you describe yourself as...	1= Male 2= Female 3= Transgender 4= Other (specify _____)	Sex2, Sex2_Text		
Sexual Orientation ^{2,3}	Do you consider yourself to be...	1= Straight or heterosexual 2= Gay or lesbian 3= Bisexual 4= OTHER (specify _____)	Sexuality, Sexuality_Text		
Page Break					
Hispanic Origin ³	Are you of Hispanic, Latino, or Spanish origin?	0= No 1 = Yes	Hisp		
Race ³	Which one of these groups would you say best represents your race?	1=White 2=Black or African American 3=American Indian or Alaska Native 4=Asian 5=Pacific Islander 6=Other	Race		
Page Break					

Construct (Source)	Question Text	Response Option	Pretest Var Name	Post 1 Var Name	Post 2 Var Name
Instruction to provide name and address	Please provide your mailing address below. This is where we will send your incentive check at the end of the study.		Instr3		
First Name	First Name	Free Response	FirstName		
Last Name	Last Name	Free Response	LastName		
Address Line 1	Street Number, Street Name	Free Response (Validity Check)	Addr1		
Address Line 2	Apartment Number, Optional Address Line 2	Free Response (Validity Check, Optional Response)	Addr2		
City	City	Free Response (Validity Check)	City		
Zip	Zip Code	Free Response	Zip		
State	State	Dropdown list 1= ALABAMA 2= ALASKA 3= ARIZONA 4= ARKANSAS 5= CALIFORNIA 6= COLORADO 7= CONNECTICUT 8= DELAWARE 9= DISTRICT OF COLUMBIA 10= FLORIDA 11= GEORGIA 12= HAWAII 13= IDAHO 14= ILLINOIS 15= INDIANA 16= IOWA 17= KANSAS 18= KENTUCKY 19= LOUISIANA 20= MAINE 21= MARYLAND 22= MASSACHUSETTS 23= MICHIGAN 24= MINNESOTA 25= MISSISSIPPI	State_0		

Construct (Source)	Question Text	Response Option	Pretest Var Name	Post 1 Var Name	Post 2 Var Name
		26= MISSOURI 27= MONTANA 28= NEBRASKA 29= NEVADA 30= NEW HAMPSHIRE 31= NEW JERSEY 32= NEW MEXICO 33= NEW YORK 34= NORTH CAROLINA 35= NORTH DAKOTA 36= OHIO 37= OKLAHOMA 38= OREGON 39= PENNSYLVANIA (40=Puerto Rico* Option not displayed, included to align with screener for phone survey participants) 41= RHODE ISLAND 42= SOUTH CAROLINA 43= SOUTH DAKOTA 44= TENNESSEE 45= TEXAS 46= UTAH 47= VERMONT 48= VIRGINIA 49= WASHINGTON 50= WEST VIRGINIA 51= WISCONSIN 52= WYOMING			
PAGE BREAK					
Time Zone	What time zone are you in?	-5=Eastern Standard Time (Ex: New York) -6=Central Standard Time (Ex: Chicago) -7=Mountain Standard Time (Ex: Salt Lake City) -8=Pacific Standard Time (Ex: Los Angeles) -9=Alaska Standard Time (Ex: Anchorage) -10=Hawaii-Aleutian Standard Time (Ex: Honolulu)	TimeZone		
PAGE BREAK					
Cell Phone Number	Do you have a cell phone?	1=Yes 0=No	Cell_YN		
PAGE BREAK					

Construct (Source)	Question Text	Response Option	Pretest Var Name	Post 1 Var Name	Post 2 Var Name
Cell Phone Number	Cell Phone Number	Free Response (Validity Check)	Phone_Number		
Page Break					
Education ³	What is the highest degree or level of school you have completed?	[0= NO SCHOOLING COMPLETED 1= NURSERY SCHOOL TO 4TH GRADE 2= 5TH OR 6TH GRADE 3= 7TH OR 8TH GRADE 4= 9TH GRADE 5= 10TH GRADE 6= 11TH GRADE 7= 12TH GRADE - NO DIPLOMA 8= HIGH SCHOOL GRADUATE - high school diploma or the equivalent (for example: GED) 9= SOME COLLEGE CREDIT, BUT LESS THAN 1 YEAR 10= 1 OR MORE YEARS OF COLLEGE, NO DEGREE 11= ASSOCIATE'S DEGREE (FOR EXAMPLE: AA, AS) 12= BACHELOR'S DEGREE (FOR EXAMPLE: BA, AB, BS) 13= MASTER'S DEGREE (FOR EXAMPLE: MA, MS, MEng, MEd, MSW, MBA) 14= PROFESSIONAL DEGREE (FOR EXAMPLE: MD, DDS, DVM, LLB, JD) 15= DOCTORATE DEGREE (FOR EXAMPLE: PhD, EdD)]	Edu		

Construct (Source)	Question Text	Response Option	Pretest Var Name	Post 1 Var Name	Post 2 Var Name
Page Break					
Age	How old are you?	Free response (Must be 3 or fewer numbers, between 18-120)	Age		
General Health ³	Would you say that in general your health is:	5= Excellent 4= Very Good 3= Good 2= Fair 1= Poor	Health		
Household ⁴	How many people are in your household, including you?	# of people [restricted to 1-10]	Household		
Income ^{4,5}	[Ask only if Household = 1, else skip to FTND 1] Which of the following categories best describes your total household income in the last 12 months?	1=Less than \$12,060 2=Between \$12,060 and \$18,089 3=Between \$18,090 and \$24,119 4=Between \$24,120 and \$30,149 5=Between \$30,150 and \$36,179 6=\$36,180 or more	Income_1		
	[Ask only if Household = 2, else skip to FTND 1] Which of the following categories best describes your total household income in the last 12 months?	1=Less than \$16,240 2=Between \$16,240 and \$24,359 3=Between \$24,360 and \$32,479 4=Between \$32,480 and \$40,599 5=Between \$40,600 and \$48,719 6=\$48,720 or more	Income_2		
	[Ask only if Household = 3, else skip to FTND 1] Which of the following categories best describes your total household income in the last 12 months?	1=Less than \$20,420 2=Between \$20,420 and \$30,629 3=Between \$30,630 and \$40,839 4=Between \$40,840 and \$51,049 5= Between \$51,050 and \$61,259 6=\$61,260 or more	Income_3		
	[Ask only if Household = 4, else skip to FTND 1]	1=Less than \$24,600 2=Between \$24,600 and \$36,899 3=Between \$36,900 and \$49,199	Income_4		

Construct (Source)	Question Text	Response Option	Pretest Var Name	Post 1 Var Name	Post 2 Var Name
	Which of the following categories best describes your total household income in the last 12 months?	4=Between \$49,200 and \$61,499 5=Between \$61,500 and \$73,799 6=\$73,800 or more			
	[Ask only if Household = 5, else skip to FTND 1] Which of the following categories best describes your total household income in the last 12 months?	1=Less than \$28,780 2=Between \$28,780 and \$43,169 3=Between \$43,170 and \$57,559 4=Between \$57,560 and \$71,949 5=Between \$71,950 and \$86,339 6=\$86,430 or more	Income_5		
	[Ask only if Household = 6, else skip to FTND 1] Which of the following categories best describes your total household income in the last 12 months?	1=Less than \$32,960 2=Between \$32,960 and \$49,439 3=Between \$49,440 and \$65,919 4=Between \$65,920 and \$82,399 5=Between \$82,400 and \$98,879 6=\$98,880 or more	Income_6		
	[Ask only if Household = 7, else skip to FTND 1] Which of the following categories best describes your total household income in the last 12 months?	1=Less than \$37,140 2=Between \$37,140 and \$55,709 3=Between \$55,710 and \$74,279 4=Between \$74,280 and \$92,849 5= Between \$92,850 and \$111,419 6=\$111,420 or more	Income_7		
	[Ask only if Household = 8, else skip to FTND 1] Which of the following categories best describes your total household income in the last 12 months?	1=Less than \$41,320 2=Between \$41,320 and \$61,979 3=Between \$61,980 and \$82,639 4=Between \$82,640 and \$103,299 5=Between \$103,300 and \$123,959 6=\$123,960 or more	Income_8		
	[Ask only if Household = 9, else skip to FTND 1]	1=Less than \$45,500 2=Between \$45,500 and \$68,249 3=Between \$68,250 and \$90,999	Income_9		

Construct (Source)	Question Text	Response Option	Pretest Var Name	Post 1 Var Name	Post 2 Var Name
	Which of the following categories best describes your total household income in the last 12 months?	4=Between \$91,000 and \$113,749 5=Between \$113,750 and \$136,549 6=\$136,500 or more			
	[Ask only if Household = 10, else skip to FTND 1] Which of the following categories best describes your total household income in the last 12 months?	1=Less than \$49,680 2=Between \$49,680 and \$74,519 3=Between \$74,520 and \$99,359 4=Between \$99,360 and \$124,199 5=Between \$124,200 and \$149,039 6=\$149,040 or more	Income_10		
Page Break					
Trust in Gov ^{3,6}	How much trust do you have in the Federal government?	5= A great deal 4= A fair amount 2= Not very much 1= None at all, or 3= No opinion	TrustGov_Pre		
Trust in FDA ^{3,6}	In your opinion, does the Food and Drug Administration, or FDA, give trustworthy information to the public?	5 = Definitely yes 4 = Probably yes 3 = Neither yes or no 2 = Probably no 1 = Definitely no	FDA_Pre		
Trust in CDC ^{3,6}	In your opinion, does the Centers for Disease Control and Prevention, or CDC, give trustworthy information to the public?	5 = Definitely yes 4 = Probably yes 3 = Neither yes or no 2 = Probably no 1 = Definitely no	CDC_Pre		
Page Break					
Nicotine Dependence ⁷	How soon after you wake up do you smoke your first cigarette?	3 = Within 5 minutes 2 = 6 – 30 minutes	FTND1_Pre	FTND1_Post1	FTND1_Post2

Construct (Source)	Question Text	Response Option	Pretest Var Name	Post 1 Var Name	Post 2 Var Name
		1 = 31-60 minutes 0 = After 60 minutes			
	Do you find it difficult to refrain from smoking in places where it is forbidden e.g. in church, at the library, in cinema, etc.?	1 = Yes 0 = No	FTND2_Pre	FTND2_Post1	FTND2_Post2
	Which cigarette would you hate most to give up?	1 = The first one in the morning 0 = All others	FTND3_Pre	FTND3_Post1	FTND3_Post2
Page Break					
Nicotine Dependence ⁷	How many cigarettes per day do you smoke?	0 = 10 or less 1 = 11-20 2 = 21-30 3 = 31 or more	FTND4_Pre	FTND4_Post1	FTND4_Post2
	Do you smoke more frequently during the first hours after waking than during the rest of the day?	1 = Yes 0 = No	FTND5_Pre	FTND5_Post1	FTND5_Post2
	Do you smoke if you are so ill that you are in bed most of the day?	1 = Yes 0 = No	FTND6_Pre	FTND6_Post1	FTND6_Post2
Page Break					
Previous Quit Attempts ⁸	How many times during the past 12 months have you stopped smoking for 1 day or longer because you were trying to quit smoking?	Dropdown (0-365)	PQA_Pre		
Quit Attempts ⁸	Since you started this study, how many times have you stopped smoking for 1 day or longer because you were trying to quit smoking?			QuitAtt_Post1 Dropdown 0-16	QuitAtt_Post2 Dropdown 0-32
Smoking Status ⁹	Do you now smoke cigarettes every day, some days or not at all?	2=Every day 1=Some days 0=Not at all	Smoke_Stat_Pre	Smoke_stat_pos t1	Smoke_Stat_post 2
Page Break					

Construct (Source)	Question Text	Response Option	Pretest Var Name	Post 1 Var Name	Post 2 Var Name
Quit Line Awareness	Do you know what national phone number you can call for help to quit smoking?	1 = Yes 0 = No (If no, skip the next question)		QLAware1	
Page Break					
Quit Line Awareness follow up	What is the national phone number?	Text Box		QLAware2	
Page Break					
Quitline Use	Since you started this study, have you called the Quitline (national phone number for help to quit smoking)?	1 = Yes 0 = No		QL_Use_Post1	QL_Use_Post2
Page Break					
Quit Intention ^{4,10}	How interested are you in quitting smoking in the next month?	4=Very interested 3=Somewhat interested 2=A little interested 1=Not at all interested	QI1_Pre	QI1_Post1	QI1_Post2
	How much do you plan to quit smoking in the next month?	4=Very much 3=Somewhat 2=A little 1=Not at all	QI2_Pre	QI2_Post1	QI2_Post2
	How likely are you to quit smoking in the next month?	4=Very likely 3=Somewhat likely 2=A little likely 1=Not at all likely	QI3_Pre	QI3_Post1	QI3_Post2
PAGE BREAK					
Quitline Intention	If you were to quit smoking in the next month, how likely are you to call the national quitline for help?		QLI_Pre	QLI_Post1	QLI_Post2
Littering Intention ⁴	How likely are you to dispose of your cigarette butts by dropping them on the ground in the next month?		LI_Pre	LI_Post1	LI_Post2
Page Break					

Construct (Source)	Question Text	Response Option	Pretest Var Name	Post 1 Var Name	Post 2 Var Name
Self Efficacy ¹¹⁻¹³	If you decided to give up smoking completely in the next month, how sure are you that you would succeed?	5=Extremely 4=Very much 3=Moderately	SE_Pre	SE_Post1	SE_Post2
Response Efficacy ¹¹	How much do you think you would benefit from health and other gains if you were to quit smoking permanently in the next month?	2=A little 1=Not at all	RE_Pre	RE_Post1	RE_Post2
PAGE BREAK					
Positive Thoughts ^{14,15}	During the past 24 hours, how often did positive thoughts about smoking come to mind (thoughts that just popped into your head, or you caught yourself thinking)?	5=All of the time 4=Often 3=Sometimes 2=Rarely 1=Never	Freq_Pos_Pre	Freq_Pos_Post1	Freq_Pos_Post2
PAGE BREAK					
Positive Thoughts ^{14,15}	[displayed if freq_pos ne never] Considering only your positive thoughts about smoking during the past 24 hours, how positive were these thoughts?	1=Not at all Positive 2=Slightly Positive 3=Moderately Positive 4=Very Positive 5=Extremely Positive	Degree_Pos_Pre	Degree_Pos_Post1	Degree_Pos_Post2
PAGE BREAK					
Negative Thoughts ^{14,15}	During the past 24 hours, how often did negative thoughts about smoking come to mind (thoughts that just popped into your head, or you caught yourself thinking)?	5=All of the time 4=Often 3=Sometimes 2=Rarely 1=Never	Freq_Neg_Pre	Freq_Neg_Post1	Freq_Neg_Post2
PAGE BREAK					
Negative Thoughts ^{14,15}	[displayed if freq_neg ne never] Considering only your negative thoughts about smoking during the past 24 hours, how negative were these thoughts?	1=Not at all Negative 2=Slightly Negative 3=Moderately Negative 4=Very Negative 5=Extremely Negative	Degree_Neg_Pre	Degree_Neg_Post1	Degree_Neg_Post2
Page Break					

Construct (Source)	Question Text	Response Option	Pretest Var Name	Post 1 Var Name	Post 2 Var Name
Current OTP Use ¹⁶	In the past 30 days, which of the following products have you used at least once? (Pick all that apply)	
 1. Cigars, cigarillos, or little cigars 2. Smokeless tobacco, for example chewing tobacco, snuff, dip, or snus 3. Electronic cigarettes, e-cigarettes, or other vaping devices 4. Water pipes or Hookah 5. Clove cigarettes 6. Roll your own cigarettes 7. None of the above [exclusive] 	OTPUse_Pre1, OTPUse_Pre2, OTPUse_Pre3, OTPUse_Pre4, OTPUse_Pre5, OTPUse_Pre6, OTPUse_Pre7		
OTP Use 2 ¹⁶	Since you started this research study, which of the following products have you used at least once? (Pick all that apply)	
 1. Cigars, cigarillos, or little cigars 2. Smokeless tobacco, for example chewing tobacco, snuff, dip, or snus 3. Electronic cigarettes, e-cigarettes, or other vaping devices 4. Water pipes or Hookah 5. Clove cigarettes 6. Roll your own cigarettes 7. None of the above [exclusive] 		OTPUse_Post1_1, OTPUse_Post1_2, OTPUse_Post1_3, OTPUse_Post1_4, OTPUse_Post1_5, OTPUse_Post1_6, OTPUse_Post1_7	OTPUse_Post2_1, OTPUse_Post2_2, OTPUse_Post2_3, OTPUse_Post2_4, OTPUse_Post2_5, OTPUse_Post2_6, OTPUse_Post2_7
Page Break					
Knowledge ^{17, 18}	Does cigarette smoke contain... (Matrix Question)	1 = Yes 0 = No 2 = Don't know	K_Inst1_Pre	K_Inst1_Post1	K_Inst1_Post2

Construct (Source)	Question Text	Response Option	Pretest Var Name	Post 1 Var Name	Post 2 Var Name
	Arsenic		K_As_Pre	K_As_Post1	K_As_Post2
	Ammonia		K_Am_Pre	K_Am_Post1	K_Am_Post2
	Formaldehyde		K_Form_Pre	K_Form_Post1	K_Form_Post2
	Lead		K_Pb_Pre	K_Pb_Post1	K_Pb_Post2
	Uranium		K_U_Pre	K_U_Post1	K_U_Post2
Page Break					
Knowledge ^{17, 18}	Does cigarette smoke cause... (Matrix Question)	1 = Yes 0 = No 2 = Don't know	K_Inst2_Pre	K_Inst2_Post1	K_Inst2_Post2
	Brain Disorders		K_BD_Pre	K_BD_Post1	K_BD_Post2
	Breathing Problems		K_BP_Pre	K_BP_Post1	K_BP_Post2
	Cancer		K_Cancer_Pre	K_Cancer_Post1	K_Cancer_Post2
	Heart Damage		K_HD_Pre	K_HD_Post1	K_HD_Post2
	Kidney Damage		K_KD_Pre	K_KD_Post1	K_KD_Post2
	Lung Tumors		K_LT_Pre	K_LT_Post1	K_LT_Post2
	Throat Cancer		K_TC_Pre	K_TC_Post1	K_TC_Post2
Page Break					
Tripartite Risk ¹⁹	If you continue smoking, how likely is it that you...	(question in matrix format)	TR1	TR1	TR1
	will get heart damage at some point in the future?	4=Very Likely 3=Likely 2=Unlikely 1=Very Unlikely	TR1_a_Pre	TR1_a_Post1	TR1_a_Post2
	will get throat cancer at some point in the future?		TR1_b_Pre	TR1_b_Post1	TR1_b_Post2
	will get lung tumors at some point in the future?		TR1_c_Pre	TR1_c_Post1	TR1_c_Post2
	will get kidney damage at some point in the future?		TR1_d_Pre	TR1_d_Post1	TR1_d_Post2
	will get breathing problems at some point in the future?		TR1_e_Pre	TR1_e_Post1	TR1_e_Post2
	will get cancer at some point in the future?		TR1_f_Pre	TR1_f_Post1	TR1_f_Post2

Construct (Source)	Question Text	Response Option	Pretest Var Name	Post 1 Var Name	Post 2 Var Name
	will get a brain disorder at some point in the future?		TR1_g_Pre	TR1_g_Post1	TR1_g_Post2
Page Break					
Tripartite Risk ¹⁹	If you continue smoking, how fearful are you...	(question in matrix format)	TR2	TR2	TR2
	of getting heart damage in the future?	4=Very fearful 3=Fearful 2=A little fearful 1=Not at all fearful	TR2_a_Pre	TR2_a_Post1	TR2_a_Post2
	of getting throat cancer in the future?		TR2_b_Pre	TR2_b_Post1	TR2_b_Post2
	of getting lung tumors in the future?		TR2_c_Pre	TR2_c_Post1	TR2_c_Post2
	of getting kidney damage in the future?		TR2_d_Pre	TR2_d_Post1	TR2_d_Post2
	of breathing problems damage in the future?		TR2_e_Pre	TR2_e_Post1	TR2_e_Post2
	of getting cancer in the future?		TR2_f_Pre	TR2_f_Post1	TR2_f_Post2
	of getting a brain disorder in the future?		TR2_g_Pre	TR2_g_Post1	TR2_g_Post2
Page Break					
Tripartite Risk ¹⁹	How much do you agree or disagree with the following statement: If I continue to smoke, I feel very vulnerable to...	(question in matrix format)	TR3	TR3	TR3
	heart damage	4=Strongly Agree 3=Agree 2=Disagree 1=Strongly Disagree	TR3_a_Pre	TR3_a_Post1	TR3_a_Post2
	throat cancer		TR3_b_Pre	TR3_b_Post1	TR3_b_Post2
	lung tumors		TR3_c_Pre	TR3_c_Post1	TR3_c_Post2
	kidney damage		TR3_d_Pre	TR3_d_Post1	TR3_d_Post2
	breathing problems		TR3_e_Pre	TR3_e_Post1	TR3_e_Post2
	cancer		TR3_f_Pre	TR3_f_Post1	TR3_f_Post2
	brain disorders		TR3_g_Pre	TR3_g_Post1	TR3_g_Post2
Page Break					
FDA Information ^{3, 6}	The Food and Drug Administration, or FDA, is the agency that ensures that food and drugs sold in this country are safe.			FDA_Info_Post1	

Construct (Source)	Question Text	Response Option	Pretest Var Name	Post 1 Var Name	Post 2 Var Name
	The FDA now regulates cigarettes and some other tobacco products. The next series of questions is about your opinions toward FDA in this role.				
FDA Credibility ^{3,6}	Do you trust the FDA to inform the public about the risks of tobacco products?	5 = Definitely yes 4 = Probably yes 3 = Neither yes or no 2 = Probably no 1 = Definitely no		Cred1_Post1	
	Is the FDA honest about the risks of tobacco products?			Cred2_Post1	
	Do you believe what the FDA says about the risks of tobacco products?			Cred3_Post1	
	Is the FDA an expert on regulating tobacco products?			Cred4_Post1	
	Is the FDA capable of doing a good job regulating tobacco products?			Cred5_Post1	
	Can the FDA effectively regulate tobacco products?			Cred6_Post1	
